## 12 Confidence Intervals, p-values and Multiplicity

All applicable statistical tests will be two-sided and will be performed using a 5% significance level; confidence intervals presented will be 95%. No adjustment will be made for multiplicity for the secondary outcomes.

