## **17 Efficacy Evaluations**

## 17.1 Data sets analysed

The principle of intention-to-treat, as far as practically possible, will be the main strategy of the analysis adopted for the primary outcome and all the secondary outcomes. These analyses will be conducted on all randomised participants, in the group to which they were allocated, and for whom the outcome(s) of interest have been observed/measured. No imputations will be made.

The membership of the analysis set for each outcome will be determined and documented and reasons for participant exclusion will be given prior to the blind being broken and the randomisation lists being requested. Reasons may include missing data, loss to follow up.

Participants to be excluded from analysis populations will be defined in template ST001TEM04: Protocol deviations and data set definitions, agreed and approved prior to any release of randomisation code.

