#### 17.4.1.1 Derivation

The CRF: *Microbiology Form* captures information on samples taken at all attended visits (scheduled and unscheduled). The variable MBDSTD gives the date the sample was taken, and the variable MBOC6C indicates that *P. aeruginosa* was cultured if it is selected (MBOC6C = "Pseudomonas aeruginosa").

Success: If there is no record of *P. aeruginosa* on a patient's microbiology CRF between 3 months and 15 months after treatment commencement.

Failure: If there is at least one record of *P. aeruginosa* on a patient's microbiology CRF between 3 months and 15 months after treatment commencement.

Any positive samp	Outcome		
<3 months	3-15 months	>15 months	
×	×	×	Success
×	×	✓	Success
✓	×	×	Success
✓	×	✓	Success
×	$\checkmark$	×	Fail
×	$\checkmark$	✓	Fail
✓	$\checkmark$	×	Fail
✓	$\checkmark$	$\checkmark$	Fail

To determine if a patient has eradicated *P. Aeruginosa* at 3 months, they must have a sample within 28 days either side of the expected 3 month visit date (treatment commencement date + 84 days) which is at least 2 days after the last date of any anti-pseudomonal treatment.

To determine if a patient has remained *P. Aeruginosa* free at 15 months, they must have either a positive sample within the primary outcome window (3-15 months) or they must have a sample within 28 days either side of the expected 15 month visit date (treatment commencement date + 420 days). Patients who have not regrown *P. Aeruginosa* and do not have a sample within the 15 month window (defined above) will not be included in the primary analysis. If a patient is withdrawn before 15 months of follow-up is completed, they will only be included in the primary outcome analysis if they have failed. If there is no evidence that they have failed prior to being withdrawn they will not be included in the primary analysis.

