#### 17.4.1.2 Analysis

The number of patients who are classified as (a) a success and (b) failure for the primary outcome (and percentages) will be presented for each treatment arm. The relative risk together with 95% confidence interval will be reported along with a two-sided p-value from a chi-squared test. The number and percentage of patients who had a positive sample at their 3-month follow-up visit will also be presented for each treatment arm.

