## **19 Additional Analyses**

#### **19.1 Sensitivity analyses of to the primary outcome analysis**

#### 19.1.1 Withdrawn patients all classified as success

Derivation and analysis as in Section 17.4.1.1 and Section 17.4.1.2 but all patients who have been followed up past 3 months but not had a sample within the 15 month window will be assumed to have not had *P. Aeruginosa*.

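### Primary analysis keeps patients without a 15-month sample only if they failed, so inclusion depends on the outcome and the relative risk is biased when such missingness differs by arm

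*SAP*

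**What the plan says.** SAP 17.4.1.1 counts any positive culture between 3 and 15 months as a failure, whether or not the patient also has a sample near 15 months. A patient without such a positive counts as a success only with a sample within 28 days of day 420. Those who have not regrown the organism and "do not have a sample within the 15 month window (defined above) will not be included in the primary analysis". For patients withdrawn before 15 months, "they will only be included in the primary outcome analysis if they have failed", and "If there is no evidence that they have failed prior to being withdrawn they will not be included in the primary analysis".

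SAP 17.4.1.2 then compares crude proportions: "The relative risk together with 95% confidence interval will be reported along with a two-sided p-value from a chi-squared test". Section 17.1 adds "No imputations will be made".

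Section 19.1 plans three sensitivity analyses that bear on this. Section 19.1.1 opens its assumption with the words "all patients who have been followed up past 3 months but not had a sample within the 15 month window will be assumed to have"; there the organism is taken to be absent, and 19.1.2 assumes the reverse for the same patients. In 19.1.3, patients followed beyond 15 months without a sample in the window are classified by their next later sample.

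**The concern.** Two patients may both lack a 15-month sample. The one with a positive culture at 6 months stays in the denominator as a failure. The one whose cultures were all negative up to month 12 is removed. Missing the 15-month sample thus removes patients not yet known to have failed and keeps those who have, which tilts each arm's proportion towards failure.

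If the tilt is the same in both arms, the harm is mainly to the reported rates. If one arm loses more 15-month samples, that arm looks worse with no true difference, and the primary relative risk and p-value are affected. The trial is open label and compares intravenous with oral treatment, so unequal follow-up is plausible, although the SAP gives no rates by arm. Section 8.9 does report that many visits fell outside their windows, so missing window samples are a practical matter in this trial.

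**Working it through.** **Inputs.** From the SAP: the inclusion rule (17.4.1.1), 1:1 allocation (8.7), chi-squared test (17.4.1.2), and section 12: "All applicable statistical tests will be two-sided and will be performed using a 5% significance level". The SAP states no sample size, success rate or dropout rate (section 10 refers to the protocol), so there is no figure of its own to reproduce. The following are assumptions:

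- p = true success probability
- m = probability of no 15-month-window sample, unrelated to outcome
- f = share of failures without that sample whose positive culture was already recorded; 0.5 and 1 are shown
- N = 150 randomised per arm

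**Step 1: one arm.** Successes kept: p(1-m). Failures kept: (1-p)(1-m(1-f)). The analysed failure proportion is failures kept divided by the sum of both. With p = 0.55 (true failure 45%):

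| m | f = 0.5 | f = 1 |
|---|---|---|
| 10% | 0.4275/(0.4275+0.495) = 46.3% | 0.45/(0.45+0.495) = 47.6% |
| 20% | 0.405/(0.405+0.44) = 47.9% | 0.45/(0.45+0.44) = 50.6% |

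At f = 0 there is no bias. At m = 5% and p = 0.5 the shift is only 0.6 to 1.3 points.

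**Step 2: direction.** If missingness is m_s in true successes and m_f in true failures, success is understated when m_s > m_f(1-f). It can reverse: with p = 0.5, m_s = 10%, m_f = 30% and f = 0.5, successes kept are 0.45 and failures kept 0.425, so analysed success is 0.45/0.875 = 0.514 against a true 0.500.

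**Step 3: equal missingness.** With no effect both arms shift alike, so the relative risk is 1.00 and the rejection rate 5.0%. With a true effect the relative risk moves slightly away from 1. Take true success of 0.60 and 0.50 (relative risk 1.20) and m = 20%. At f = 0.5 the analysed rates are 0.571 and 0.471, ratio 1.214. At f = 1 they are 0.545 and 0.444, ratio 1.227. The odds ratio stays at 1.5.

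**Step 4: unequal missingness, no effect.** With p = 0.55 and 5% versus 25% missing:

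- f = 0.5: success 0.5225/0.96125 = 0.5436 against 0.4125/0.80625 = 0.5116, relative risk 1.06
- f = 1: 0.5225/0.9725 = 0.5373 against 0.4125/0.8625 = 0.4783, relative risk 1.12

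Type I error uses the normal approximation to the chi-squared test: the chance that the difference exceeds 1.96 pooled standard errors in either direction. For p = 0.5, 5% versus 25% and f = 1, the rates are 0.4872 (n = 146.25) and 0.4286 (n = 131.25). The difference is 0.0586, the pooled standard error 0.0599 and the rejection probability 16.4%. At 150 per arm:

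| Missing | f = 0.5 | f = 1 |
|---|---|---|
| 5% vs 15% | 5.7% | 7.5% |
| 10% vs 20% | 5.8% | 7.8% |
| 5% vs 25% | 8.1% | 16.4% |

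The figures for p = 0.55 agree to the precision shown.

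**Step 5: planned sensitivity analyses.** No effect, p = 0.5, 5% versus 20% missing, f = 0.5, recoding only patients whose outcome is undetermined. Successes kept are 0.475 and 0.400; undetermined patients are 0.0375 and 0.150.

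- Primary analysis: 1.05
- All success (19.1.1): 0.5125/0.550 = 0.93
- All failure (19.1.2): 0.475/0.400 = 1.19
- Opposite directions: 0.475/0.550 = 0.86 and 0.5125/0.400 = 1.28

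**Step 6: does the fix work?** In a simulation with 400,000 patients per scenario, three-monthly cultures, non-informative dropout and true success of about 0.495, the SAP rule gave 0.486, 0.477, 0.459 and 0.436 at 5%, 10%, 20% and 30% without a 15-month sample. Kaplan-Meier at 15 months with censoring at the last culture gave 0.494-0.496 throughout.

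**The case against.** The strongest defence is that the size is unknown and may be small. A reader might infer that the rule removes only would-be successes. That holds only at f = 1: the rule also removes patients who would have regrown the organism later, so the upper ends of the ranges are a worst case. Nor do the documents support saying that the test is invalid whatever the missingness. It holds its level when missingness is equal and there is no effect, and nothing in the SAP establishes 5% versus 25%. All of this stands.

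The SAP also takes mitigating steps. The 28-day window either side of day 420 is wider than the general window for that visit in 8.9. Section 14.2 sends patients with incomplete primary data to blind review, and 17.1 fixes analysis-set membership before the randomisation lists are requested. These steps limit missingness and discretion, but they do not alter a rule that itself selects on outcome.

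On the sensitivity analyses, it would be too strong to say that they tell us nothing about a difference between arms. When missingness is unequal, 19.1.1 and 19.1.2 move the relative risk to either side of the primary result, which would signal the problem. What they do not give is the extreme between-arm range.

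A reader might also infer that 19.1.1 turns recorded regrowths into successes, since its wording covers everyone without a sample in the window. The text does not support that as the intent. The heading refers to withdrawn patients, the derivation in 17.4.1.1 is retained, and the change log describes the amendment as bringing further patients in. It is a wording ambiguity.

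**Conclusion.** The point holds. Inclusion in the primary analysis depends on the outcome, and nothing in 17.4.1.2 or 17.1 corrects for it. If missingness is unrelated to outcome, success is understated in both arms, by about 1 to 3 percentage points at 10% missing and 3 to 6 at 20%. The direction can reverse if undetected future failures drop out much more often than successes. The relative risk and test are distorted under no effect only when missingness differs by arm: little at 5% versus 15%, materially at 5% versus 25%. With a true effect the relative risk shifts slightly even when missingness is equal.

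The three sensitivity analyses partly expose this but do not correct the primary estimate. 19.1.1 and 19.1.2 recode both arms in the same direction and omit patients not followed past 3 months; 19.1.3 reaches only those followed beyond 15 months. All sizes rest on assumed failure rates, missingness, f and 150 per arm, so the effect in this trial is undetermined until missingness by arm is known.

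**What to change.** Make inclusion independent of outcome.

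- **Preferred.** Estimate each arm's 15-month probability of remaining free of the organism by Kaplan-Meier. Include every patient with at least one culture in or after the T3 window, count a positive T3-window culture as failure at T3, and censor patients without regrowth at their last negative culture. Report the ratio of the two probabilities with a 95% CI and a matching test. Entry must not require a culture after T3, or a patient whose only culture is a positive one at T3 would be lost.
- **Alternative.** Keep the yes/no outcome and multiply impute 15-month status for undetermined patients, amending the no-imputation sentence in 17.1.
- **Sensitivity analyses.** Keep the current rule as one of them. State in 19.1.1 and 19.1.2 that only patients without a recorded positive at 3-15 months are recoded, and include those lost before 3 months. Add two opposing cases: undetermined IV patients as successes with undetermined oral patients as failures, and the reverse.

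The cost is SAP wording, a check against the protocol's definition of the primary analysis, and modest programming. Sample dates are already collected and Kaplan-Meier is already planned in 17.4.2.1.2. The downside is that the main estimate assumes non-informative censoring, or data missing at random if imputed. The opposing cases test that assumption, and they also cover patients with no culture from T3 onwards, whom Kaplan-Meier cannot include.

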#### 8.9 Schedule of assessments

Table 3 in Section 7 of the protocol outlines the schedule of assessments.

Note that for the purpose of this trial, a 'month' is defined as 28 days. Visits should have occurred as follows:

	Scheduled study visit	Time after treatment start
T 3	3 months	12 weeks
$T_6$	6 months	24 weeks
T 9	9 months	36 weeks
T 12	12 months	48 weeks
T 15	15 months	60 weeks
T 18	18 months	72 weeks
T 21	21 months	84 weeks
T 24	24 months	96 weeks

Due to large numbers of visits occurring outside of appropriate visit windows and not consistently being captured on scheduled or unscheduled visit CRFs; where outcomes refer to specific time points, data will be included based on dates of assessments rather than CRF names. For an assessment to be associated with a particular time-point it must have occurred within 1 week either side of the expected visit date, apart from  $T_{15}$  which may be minus 1 week or plus 2 weeks of the expected visit date.

Not all patients were followed up after  $T_{15}$ .  $T_{18}$ ,  $T_{21}$  and  $T_{24}$  were proposed in the protocol up to and including version 7. Patients randomised after 1st January 2016 were required to complete up to and including  $T_{15}$  only.

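### Read literally, the withdrawal sentences in SAP 17.4.1.1 drop a patient with a valid early T15 negative who withdraws before day 420; limit them to patients with no T15-window sample (minor)

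*SAP*

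**What the plan says.** The rules are in SAP section 17.4.1.1 (primary outcome, Derivation), with supporting definitions elsewhere.

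- **Success or failure.** This depends on whether *P. aeruginosa* is recorded on the "microbiology CRF between 3 months and 15 months after treatment commencement".
- **Window rule.** To be judged free of infection at 15 months, a patient with no positive in that period qualifies as follows: "they must have a sample within 28 days either side of the expected 15 month visit date". That date is treatment commencement plus 420 days.
- **Exclusion for a missing sample.** Patients without regrowth who "do not have a sample within the 15 month window (defined above) will not be included in the primary analysis".
- **Withdrawal rule.** For anyone who leaves the trial before finishing 15 months, the SAP says that "they will only be included in the primary outcome analysis if they have failed". The next sentence repeats the rule from the other side: no evidence of failure before withdrawal means exclusion.
- **Month length.** Section 8.9 states that "for the purpose of this trial, a 'month' is defined as 28 days" and places T15 at 60 weeks.
- **Sensitivity analyses.** Sections 19.1.1 and 19.1.2 reclassify patients "followed up past 3 months but not had a sample within the 15 month window". Section 19.1.3 adds patients followed beyond 15 months who also lack that sample.
- **General principles.** Section 8.4.3 keeps data collected before withdrawal unless the patient objects. Section 17.1 analyses all randomised participants whose outcome was observed.

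**The concern.** The window opens 28 days before the 15-month date, so a patient can supply the sample that settles the outcome and still withdraw before that date. The window rule makes such a patient assessable. The withdrawal rule, taken at its word, removes the patient unless a failure has been recorded.

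The removal depends on the outcome. A patient with a positive culture at the same time stays in as a failure, and a patient with a negative culture leaves. A rule that can delete observed successes but never observed failures lowers the success rate in any arm where it operates. Two programmers could also code the paragraph differently and obtain different primary analysis sets.

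**Working it through.** **Inputs.** Month = 28 days and T15 = 60 weeks (section 8.9); T15 window = 28 days either side of commencement + 420 days (section 17.4.1.1). The SAP gives no sample size, success rate or count of late withdrawals, so the size calculation below uses assumed figures.

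**1. The SAP's own date.** 15 × 28 = 420 and 60 × 7 = 420, which agrees with the stated 420 days.

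**2. Window.** 420 − 28 = 392 and 420 + 28 = 448. The days before day 420 run from 392 to 419, which is 28 days.

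**3. Classification.** The cases that matter, taking completion of 15 months as day 420:

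| Positive in 3-15 months | T15-window sample | Withdrawal | Window rule | With withdrawal rule added |
|---|---|---|---|---|
| No | Day 392-419 | None | Success | Success |
| No | Day 392-419 | After sample, before day 420 | Success | **Excluded** |
| No | Day 392-419 | Day 425 | Success | Success |
| No | None | Before day 420 | Excluded | Excluded |
| Yes | Day 392-419 | After sample, before day 420 | Fail | Fail |
| Yes | None | Before day 420 | Fail | Fail |

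Only the second row changes. Every patient with a positive in 3-15 months is a Fail either way, so the discrepancy can remove successes only.

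**4. Sensitivity analyses.** Sections 19.1.1, 19.1.2 and 19.1.3 each require that the T15-window sample be absent. The patient in the second row has it, so none of the three brings that patient back.

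**5. Size, on assumed figures.** Take n analysed patients in an arm, s successes, and k affected patients dropped. The success rate becomes (s − k)/(n − k).

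- n = 130, s = 65, k = 1: 64/129 = 49.6%, against 65/130 = 50.0%. If the other arm loses nobody and also has 50.0%, the relative risk goes from 1.00 to 0.99.
- Over n = 100 to 130 and true success of 40% to 60%, one dropped patient costs between 0.3 points (78/130 = 60.0% to 77/129 = 59.7%) and 0.6 points (40/100 = 40.0% to 39/99 = 39.4%).
- One dropped from each arm, both at 65/130: (64/129)/(64/129) = 1.00, unchanged. If the arms differ, say 78/130 and 65/130, the relative risk goes from 78/65 = 1.200 to 77/64 = 1.203, which is negligible.

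**The case against.** The strongest reply is that section 17.4.1.1 does not define completion of 15 months of follow-up in days. The SAP also describes follow-up as visits completed: section 8.9 says patients randomised after 1 January 2016 had to complete visits up to T15 only, and it allows T15 assessments to fall up to a week early. A patient who attends T15 early and gives the sample can fairly be said to have finished. On that reading the discrepancy shrinks to a patient with, for example, an unscheduled negative on days 392-419 who withdraws before the T15 visit. The context supports this: the withdrawal sentences directly follow the missing-sample exclusion, and 19.1.1 and 19.1.2 carry headings about withdrawn patients while their text describes patients lacking the sample. This is a reasonable reading and may be the intended one, but the SAP does not state it, and its only numerical definition gives day 420.

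A second reply is that having the sample is a necessary condition, not a promise of inclusion, so the two rules could simply be cumulative. That weakens any charge of strict contradiction. It leaves an exclusion that depends on the outcome and sits badly with 8.4.3 and 17.1.

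A third reply is procedural. Section 14.2 sends patients with incomplete primary outcome data to blind review, and section 17.1 requires analysis-set membership to be documented before the randomisation lists are requested. These safeguards limit selective handling and should be credited. They do not settle what the sentence means, and whether this patient counts as incomplete under 14.2 turns on the same ambiguity.

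**Conclusion.** The point holds as a drafting gap in the primary-outcome rule. Followed literally, the withdrawal sentences exclude an observed success that the window rule would count, and no sensitivity analysis recovers it. The result rests on reading completion of 15 months as day 420. The alternative reading, T15 visit not done, removes most of the problem, and the SAP does not choose between them.

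A reader might infer more: that the section flatly contradicts itself, or that the treatment comparison is materially biased. The first goes too far because of the alternative reading. The second would need several such patients concentrated in one arm. Six in one arm, for instance, would give (65 − 6)/(130 − 6) = 59/124 = 47.6% and a relative risk of 0.95, but nothing in the SAP supports such a count or any difference between arms. The patient must meet three conditions together: no positive in 3-15 months, a negative on days 392-419, and withdrawal after that sample but before day 420. The number is probably very small, and one patient is worth about 0.4 points on the assumed 65/130. In practice the comparison is biased only if such withdrawals differ between arms.

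Severity: minor.

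**What to change.** Add one condition to the withdrawal sentence in 17.4.1.1, so that it begins: "If a patient is withdrawn before 15 months of follow-up is completed" *and has no sample within the T15 window*, and continues as now. Limit the sentence after it to the same patients. Any patient with a T15-window sample is then classified from the samples whatever the withdrawal date, subject only to the exception in 8.4.3 for patients who ask that their data not be used. This agrees with 8.4.3 and 17.1 and gives the same answer under both readings of completed follow-up.

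The cost is one clause in the SAP and the matching line in the derivation program. No new data are needed, and no patient who lacks the sample is treated differently.

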#### 17.4.1.2 Analysis

The number of patients who are classified as (a) a success and (b) failure for the primary outcome (and percentages) will be presented for each treatment arm. The relative risk together with 95% confidence interval will be reported along with a two-sided p-value from a chi-squared test. The number and percentage of patients who had a positive sample at their 3-month follow-up visit will also be presented for each treatment arm.

#### 17.4.2 Secondary outcomes

#### 17.4.2.1 Time to reoccurrence of original *P.aeruginosa* infection

Only patients who have a baseline sample and at least one sample post three months will be included in this analysis.

